7.2 Study Drug Administration

Study drug administration for both Adagen[®] and EZN-2279 will be summarized. Duration of treatment (days treated) is the number of days on each treatment based on the first and last days of treatment with each study drug (last day of study drug – first day of study drug + 1). The number and percent of patients and the number of doses within categories for weeks on treatment will be summarized for Adagen[®]. The percent of patients and the number of doses within categories for months of treatment for EZN-2279 during the EZN-2279 treatment period, and months of treatment combining the EZN-2279 treatment and maintenance periods will be summarized with categories. Duration of treatment (days) will also be summarized as a continuous variable for Adagen[®], EZN-2279 treatment, and overall EZN-2279 (treatment plus maintenance) using descriptive statistics.

Administration of both Adagen[®] and EZN-2279 will be listed.

7.3 Adverse Events and Other Complications

All adverse events will be coded using the Medical Dictionary for Regulatory Activities (MedDRA) Version 16.0 or the most recent version prior to database lock. Summaries will be presented for all treatment-emergent adverse events (overall and by severity), adverse events determined by the investigator to be treatment-related (overall and by severity), serious adverse events (SAEs), adverse events causing discontinuation from study, adverse events causing discontinuation from study drug, and non-serious adverse events. In addition to being summarized as adverse events, infectious complications and hospitalizations are considered efficacy measures as are summarized in Section 6.3.

The frequency of adverse events will be summarized using descriptive statistics by system organ class (SOC), preferred term and study drug group. Patients are counted only once in each SOC category, and only once in each preferred term category.

Treatment-related adverse event summaries will include adverse events with missing relationship to study drug. For the summaries by severity, patients are counted at the greatest severity. Adverse events missing the flag indicating serious will be excluded from the summary of serious adverse events but included in the summary of non-serious adverse events.

There will be two treatment emergent adverse event summaries provided: all treatment emergent adverse events while the patient takes Adagen[®] study drug and all treatment emergent adverse events while the patient takes EZN-2279, where treatment emergent are new or worsening adverse events that occur while on the respective therapies.

Listings for all adverse events, deaths, serious adverse events, adverse events leading to discontinuation, MedDRA dictionary terms for adverse event descriptions, and adverse event preferred terms by patient number will be presented.

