### 10.4.4. Adverse Event Assessment

The patients will be instructed to inform the PI or his/her designee of any AEs occurring during the study. All AEs whether observed by the PI or his/her designee, elicited by the PI or his/her designee (e.g., via physical examination findings or review of laboratory results), or spontaneously reported by the patient will be documented in the patient's medical record/chart.

Patients will be questioned in an open manner (e.g., "how do you feel?", "any changes since your last visit?") regarding any new adverse events that may have occurred. Patients will also be specifically questioned regarding the status of ongoing adverse events. For each adverse event the following information will be recorded:

- Onset date and time
- Resolution date and time
- Severity/intensity (see section 12.2.5)
- Relationship to study drug (see section 12.2.4)
- Serious or non-serious (see section 12.2.3)

- Actions taken to manage/treat the event
- Outcome of the event - resolved, resolved with sequelae, ongoing, death

All AEs should be followed until they are resolved or until a stable clinical endpoint is reached. Any

SAE should be reported to Leadiant Biosciences Drug Safety Surveillance (see Study

Reference

Manual for contact information).

Any patient withdrawn due to any AE (whether serious or non-serious) or clinically significant abnormal laboratory test value will be evaluated by the PI or his/her designee, or a monitoring physician, and will be treated and/or followed up until the symptom(s) or value(s) return to normal/Baseline or acceptable levels, as judged by the PI.

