#### 10.5.3.2. Hospitalizations

If a patient is hospitalized, the reason for and the duration of each hospitalization will be recorded.

All hospitalizations should be reported to Leadiant Biosciences Drug Safety Surveillance (see Study Reference Manual for contact information).

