10.4 Screening, Baseline and Study Weeks

No windowing schemes will be applied to the data. For by-visit summaries, if there are multiple assessments at a post baseline visit then the last non-missing assessment at that visit will be used for the summary. This includes assessments at the scheduled and unscheduled visits. For Patients who withdraw from the study, data at the early termination visit will be excluded from the by-visit summaries but will be included in the endpoint summaries.

Screening is defined as the last measurement for a variable before the initial dose of Adagen[®] study drug. With the exception of adverse events and medications, assessments collected at the screening visit are associated with the screening period because Adagen[®]

is not administered until all procedures are complete. Adverse events and medications starting on the day of the first dose of Adagen[®] are associated with Adagen[®] treatment.

Baseline is defined as the last measurement for a variable before the initial dose of EZN-2279 study drug, and is only used as the starting point for efficacy endpoints. With the exception of adverse events and concomitant medications, assessments collected at EZN-2279 Day-1 (Week T-1) are associated with Adagen[®] treatment because EZN-2279 is not administered until all procedures are complete. Adverse events and concomitant medications starting on the day of the first dose of EZN-2279 are associated with EZN-2279 treatment.

With regard to screening and baseline determination, assessments falling exactly on the date of the first dose of each study medication will be considered pre-dosing for that medication with the exception of adverse events and concomitant medications, which will be associated with the respective study drug.

Missing data will not be imputed.

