10.6 Safety Data Handling

For the purposes of AE reporting, three time periods will be defined based upon the onset date of the AE:

- “Pre-treatment AEs” are AEs with onset dates < date of the first dose of Adagen[®] study medication.
- “Treatment-emergent AEs” are AEs with onset dates \geq date of the first dose of study medication and within 30 days following the date of the last dose of study medication.
- “Post-treatment AEs” are AEs with onset dates > 30 days after the date of the last dose of study medication, within study STP-2279-002.

“Pre-treatment” and “Post-treatment” AEs are considered non-treatment-emergent AEs. For AEs with partially missing onset dates, an onset date is imputed as detailed in Section 12 (Programming Specifications). If an AE has a completely missing onset date, it is

counted as a “treatment-emergent” event, unless the stop date is on or before the date of the first dose of study medication.

If relationship to study drug is missing, for analysis purposes it will be assumed to be related to study drug. For AEs which occur more than once within a time period (see above), the AE which is most related to study drug in that time period will be used in the summary of AEs by categories of relationship to study drug. Similarly, the AE with the maximum intensity in that time period will be used in the summary of AEs by categories of severity.

For each study drug (EZN-2279 or Adagen[®]) medications will be assigned to a time period as follows:

- Medications taken any time < date of the first dose of Adagen[®] during the Lead-in phase will be considered prior medications.
- Medications can be concomitant with either Adagen[®], EZN-2279, or both. Medications taken any time \geq date of the first dose of respective study medication and within 30 days following the date of the last dose of respective study medication will be considered concomitant medications for that study drug.
- Medications taken > 30 days after the date of the last dose of respective study medication will be considered “post treatment” medications for that study drug.

Note that medications can be counted in more than one category (i.e., prior/concomitant) and can have different assignments for different study drugs. Imputation rules for partially missing start/stop dates are described in Section 12 (Programming Specifications).

Change from baseline to Week X in safety endpoints will be calculated as:

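### SAP 7.3 tabulates adverse events with a missing seriousness flag as non-serious, against the direction of its other missing-data rules for adverse events, so the rule can lower the SAE count but never raise it

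*SAP*

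**What the plan says.** SAP 7.3 gives a two-part rule for an adverse event whose seriousness field is blank. The first part is "Adverse events missing the flag indicating serious will be excluded from the summary of serious adverse events"; the second is "but included in the summary of non-serious adverse events".

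The same paragraph handles blank causality in the opposite direction: "Treatment-related adverse event summaries will include adverse events with missing relationship to study drug". SAP 10.6 repeats this: "If relationship to study drug is missing, for analysis purposes it will be assumed to be related to study drug". SAP 10.6 also says that an event with a completely missing onset date is "counted as a “treatment-emergent” event, unless the stop date is on or before the date of the first dose of study medication".

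Protocol 13.2.4 leaves the handling of missing data to the SAP, so no protocol rule competes. Protocol 12.2.3 defines seriousness by outcome, including death and in-patient hospitalisation, in the view of the investigator or the sponsor.

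The trial collects data that bear on those outcomes. Protocol 10.4.4 records the outcome of each event, with death as one category. Protocol 10.5.3.2 says: "If a patient is hospitalized, the reason for and the duration of each hospitalization will be recorded". Protocol 10.5.3.4 records the date of and reason for any death. Protocol 12.4 requires SAE reports to the sponsor.

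**The concern.** A rule for missing safety data should either stay neutral or lean toward showing the event. For causality and timing the SAP leans toward showing it. For seriousness it leans the other way and gives no reason.

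The rule also takes no account of the rest of the record. Read literally, an event with a fatal outcome and a blank flag would appear in the non-serious table, although the case report form holds what is needed to classify it.

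SAEs are among the secondary safety endpoints, and protocol 5.3.2 says that EZN-2279 had not been studied clinically before. With about six patients, one event can decide whether the summary shows one patient with an SAE or none.

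**Working it through.** There is no stated figure to reproduce, so the check compares the rules and then works out the direction and size of any error.

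**Direction of each default**

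| Missing item | Where | Default | Direction |
|---|---|---|---|
| Relationship to study drug | SAP 7.3, 10.6 | Related | Conservative |
| Onset date, completely missing | SAP 10.6 | Treatment-emergent, unless the stop date rules it out | Conservative |
| Onset date, partial | SAP 11 | Where the known part fits the start of lead-in dosing, set to the first dosing day | Conservative |
| Seriousness flag | SAP 7.3 | Non-serious | Favourable to the drug |

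**Bounds.** Let N be the number of patients in the table, k the number with at least one flagged SAE, and m the number of further patients whose only potentially serious event has no flag. Take completed flags as correct.

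- Reported by the SAP: k/N.
- Value with all flags complete: between k/N and (k + m)/N.
- Error of the SAP figure: between 0 and −m/N, never positive. The non-serious table can only be inflated or unchanged.

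**Size per affected patient.** SAP 3.2 plans six evaluable patients and allows more to be enrolled. SAP 7 uses the as-treated set, which SAP 4.1 defines as anyone with at least one dose of either drug. With m = 1:

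- N = 6: 1/6 = 16.7 points.
- N = 7: 1/7 = 14.3 points.
- N = 8: 1/8 = 12.5 points.

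At N = 6, with exact (Clopper-Pearson) 95% limits:

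- k = 0: 0/6 = 0.0% (0 to 45.9%) is reported where 1/6 = 16.7% (0.4 to 64.1%) may be true.
- k = 1: 1/6 = 16.7% is reported where 2/6 = 33.3% (4.3 to 77.7%) may be true.

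The intervals overlap heavily. What changes materially is the count, for example none instead of one.

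**How likely.** The documents give no rate of missing flags. As an assumption only, let each truly serious event have probability p of still lacking its flag at analysis, independently, with p from 5% to 20%. The chance that at least one of s events drops out of the SAE summary is 1 − (1 − p)^s:

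- s = 1: 5% to 20%.
- s = 2: 1 − 0.95² = 9.8% to 1 − 0.80² = 36%.
- s = 3: 1 − 0.95³ = 14.3% to 1 − 0.80³ = 48.8%.

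If every flag is complete, p = 0 and the rule has no effect.

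**The case against.** The best defence is that the rule will rarely operate and that little is hidden when it does. Protocol 10.4.4 and 12.3 require seriousness for each event. Protocol 14.6.2 provides checks for missing data and a quality audit before lock. Hospitalisations and deaths go to the sponsor's drug safety group under protocol 10.5.3.2 and 10.5.3.4. SAP 7.3 lists all adverse events and deaths, and SAP 6.3.4 summarises hospitalisations and survival separately. All of this stands and makes the expected effect small. None of it decides where an unflagged event goes in the summary tables.

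A second defence is the statement in SAP 10.4, "Missing data will not be imputed". It does not help: putting an unflagged event in the non-serious table is already a classification. A separate missing row would be neutral, and SAP 11 provides for a missing category in categorical tables.

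A third is that counting blanks as serious only reverses the error. That is fair for flags that nobody tries to resolve, which is why resolution should come first.

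A reader might also infer two stronger points that the documents do not support:

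- **That DSMC reviews depend on this table.** Protocol 12.4 has the sponsor forward all SAE reports to the DSMC, so the committee has a direct source.
- **That the error is 1/3 = 33.3 points at the BLA cut.** Three patients with data through Week T-21 trigger that cut, but SAP 6.4 and 10.1 include everyone enrolled at the time. SAP 10.1 describes listings, and SAP 6.4 leaves the analysis to a separate BLA analysis plan. Whether this rule applies there is not known.

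**Conclusion.** The point holds as an inconsistent, one-directional default. The SAP resolves missing causality and onset dates toward showing the event and missing seriousness away from it, and it does not use the collected outcome, hospitalisation, death or SAE-report data to settle the flag.

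It would go too far to conclude that the SAE table will be understated. The rule can understate it. The 16.7-point figure needs all of the following: exactly six treated patients in the table, a truly serious event, a flag still missing at analysis, and no other flagged SAE in that patient. Within a single table row there is also no effect if the patient already has a flagged SAE there, because SAP 7.3 counts each patient once per system organ class and once per preferred term. With more treated patients the figure is smaller; with complete flags it is zero.

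Given the controls in the protocol, the expected effect is probably small. The change is still worth making because it is cheap and removes a default that errs only in the drug's favour.

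**What to change.** Replace the sentence in SAP 7.3 with a rule that applies to missing flags only:

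1. Before each analysis, resolve every missing seriousness flag against the protocol 12.2.3 criteria, using the AE outcome, the hospitalisation and death records, and the SAE reports.
2. Count any event whose flag is still missing as serious, with a footnote marking it as imputed.
3. Remove such events from the non-serious table.

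The rule should not override a completed non-serious entry, even where a hospitalisation or death is on record. Protocol 12.2.3 rests seriousness on the view of the investigator or sponsor, so an apparent conflict there is a data query and not a programming step.

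The cost is a short edit to one SAP section, a footnote and the resolution step. No new data are needed. The downside is that a non-serious event may occasionally appear as serious until its query is answered; the footnote makes this visible, and it is reversed when the answer arrives.

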#### 10.7.1.2. EZN-2279

EZN-2279 will be administered starting after completion of the Adagen® Lead-in phase. Patients will be transitioned to receive an equivalent dose of EZN-2279 as a weekly i.m. injection. Based upon 1 mg EZN-2279 containing ADA enzymatic activity of 150 U of Adagen®, the equivalent dose of EZN-2279 will be calculated as follows:

$$\text{Adagen® dose (U/kg)} \times 1\text{mg EZN-2279}/150\text{U Adagen®} = \text{EZN-2279 dose (mg/kg)}$$

For example, for a 50 kg patient on a dose of 30 U/kg of Adagen®:

$$\text{Adagen® 30 U/kg} \times \frac{1 \text{ mg EZN-2279}}{150 \text{ U Adagen®}} = 0.2 \text{ mg/kg EZN-2279}$$

$$50 \text{ kg} \times 0.2\text{mg/kg} \times 1 \text{ mL}/1.6 \text{ mg} = 6.25 \text{ mL (10 mg)}$$

The date and time of each dose administered will be recorded.

All patients will be observed for at least 1 hour after administration of EZN-2279 for doses administered at the study site through study Week T-9.

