#### **11.4. EZN-2279 Maintenance Period**

As part of standard clinical care, the following evaluations will be performed during visits approximately every 3 months (13 weeks  $\pm$ 3 weeks) until study completion. For example, based upon the start of EZN-2279 treatment (Day 1, Week T-1), maintenance visits would be scheduled to occur on Weeks 34 (Cycle 1), 47 (Cycle 2), 60 (Cycle 3), 73 (Cycle 4), 86 (Cycle 5), 99 (Cycle 6), 112 (Cycle 7), 125 (Cycle 8), 138 (Cycle 9), 151 (Cycle 10), 164 (Cycle 11), 177 (Cycle 12), 190 (Cycle 13)  $\pm$ 3 weeks from start of EZN-2279 treatment.

The patient will have the following procedures performed at each maintenance visit prior to EZN-2279 dosing:

- Physical examination
- Height and weight for growth assessment
- Performance status
- Vital Signs
- Safety Lab
  - Hematology
  - Chemistry
  - Urinalysis
- Other labs – blood samples will be obtained 15 to 30 minutes prior to dosing for:
  - dAXP
  - Trough ADA activity
  - B-, T-, and NK-lymphocyte subset analysis
  - Quantitative immunoglobulins
  - EZN-2279 antibody titers (i.e., neutralizing and binding antibodies) and anti-PEG antibodies
- Adverse event assessment
- Assessment of infectious complications and hospitalizations
- Review of EZN-2279 administration diary card and returned vials for assessment of treatment compliance
- Assessment of concomitant medications and procedures since last study visit

- Assessment of overall survival

An appropriate supply of EZN-2279 will be dispensed along with a medication compliance diary card. Note that it is not necessary to dispense a full 13 week supply during a maintenance visit; quantities of EZN-2279 dispensed will be at the discretion of the Investigator based upon the patient's proximity to the study site and medication compliance.

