### 13.2.3.5. Safety Data Analysis

Adverse Events and Serious Adverse Events – AEs will be categorized using Medical Dictionary for Regulatory Activities (MedDRA) Version 10.0 or later. The intensity of toxicities will be graded by the Investigator as mild, moderate, or severe as described in Section 12.2.5. Serious Adverse Events (SAEs) will be a subset of the overall AE analysis and may be analyzed in a similar manner.

The calculation of AE incidence will be based on the number of patients per AE category. For each patient who has multiple AEs classified to the same category, that patient will be tabulated under the maximum toxicity intensity for that AE category. The incidence of AEs will be tabulated by MedDRA system organ class and preferred term, as well as by treatment group.

An AE onset between the date of the first dose of study drug and 30 days after the last dose of study drug is considered as a treatment-emergent AE.

- Laboratory Safety Data – Hematology, chemistry, and urinalysis data will be summarized by timepoint of collection and by treatment group. In addition, out-of-normal range values will be listed.
- Other Safety Data – the results of antibodies against EZN-2279, antibodies against Adagen®, and antibodies against PEG will be summarized. The relationships between immunogenicity, PK, and the clinical toxicities will be examined as appropriate.

Concomitant medications and findings in physical examinations will be described textually as recorded in the CRF.

Descriptive statistics of vital signs measurements as well as changes from baseline will be tabulated.

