7. SAFETY ANALYSIS

The as-treated population will be used for all of the safety analyses. Summaries will be presented by study drug group (EZN-2279 or Adagen[®]), if appropriate, through completion of the EZN-2279 maintenance period. All safety data will be listed.

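### The two adverse-event summaries in SAP 7.3 are not comparable: they differ in exposure and in how often events are asked about, and the EZN-2279 summary is not split by period

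*SAP*

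**What the plan says.** SAP 7.3 defines the summaries by drug alone: "There will be two treatment emergent adverse event summaries provided", namely "all treatment emergent adverse events while the patient takes Adagen[®] study drug and all treatment emergent adverse events while the patient takes EZN-2279". SAP 7 presents safety by drug group, "if appropriate, through completion of the EZN-2279 maintenance period". Neither section separates EZN-2279 treatment from EZN-2279 maintenance for adverse events (AEs). SAP 7.2 does make that distinction for exposure: it summarises days on Adagen, days in EZN-2279 treatment, and days on EZN-2279 overall.

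The measure is a count of patients. SAP 7.3: "Patients are counted only once in each SOC category, and only once in each preferred term category". Protocol 13.2.3.5: "The calculation of AE incidence will be based on the number of patients per AE category". Neither document plans a rate per unit of patient-time.

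AE assessment follows the visit schedule:

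- **Adagen lead-in** (Protocol 7.1.1, 11.2.2): weekly visits for at least 3 weeks.
- **EZN-2279, T-1 to T-11** (Protocol 11.3.1 to 11.3.12): weekly.
- **EZN-2279, T-13 to T-21** (Protocol 11.3.13 to 11.3.22): every two weeks. The even-numbered weeks T-12 to T-20 may be home doses, and no AE assessment is listed for them.
- **EZN-2279 maintenance** (Protocol 11.4): "the following evaluations will be performed during visits approximately every 3 months (13 weeks", with a window of 3 weeks either way. The diary reviewed at these visits records dosing.

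Post-dose observation also differs. Protocol 10.7.1.2: "All patients will be observed for at least 1 hour after administration of EZN-2279", for doses given at the site through T-9. For Adagen, Protocol 10.9 states post-dose monitoring only for the initial lead-in dose.

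**The concern.** Safety and tolerability is a secondary objective, and these two summaries are the only AE tables by drug that the SAP describes. Readers will set them side by side, since each patient is meant to serve as his or her own control.

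Two differences stand between them and a fair reading. EZN-2279 exposure is much longer, which raises the chance that a patient has at least one event of any kind. In addition, most EZN-2279 time in the long run is maintenance time, when patients are asked about events about once a quarter. Mild events that resolve quickly are the ones most likely to be missed there. The first difference pushes the planned percentages up. The second would push a rate down if a reader adjusted for exposure. Opposing distortions of unknown relative size do not cancel, so neither reading gives a clean contrast with Adagen.

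**Working it through.** **1. The schedule.** Protocol 11.4 lists maintenance visits from the first EZN-2279 dose. Week = 21 + 13k for k = 1 to 13 gives 34, 47, 60, ..., 190, which matches the listed weeks. Cycle 2 is week 47, the one-year analysis in SAP 6.1 and 7.1. Protocol 7.4.1 expects about 2 to 3 years of treatment, or 104 to 156 weeks.

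**2. Exposure.** Against the minimum 3-week lead-in, the ratio is 21/3 = 7 at the end of the treatment period, 47/3 = 16 at week 47, 104/3 = 35 and 156/3 = 52. A longer lead-in lowers these ratios.

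**3. The planned measure.** Assume the same constant event rate r per week on both drugs. The expected share of patients with at least one recorded event is:

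- Adagen: 1 − exp(−rL), with L the lead-in in weeks.
- EZN-2279: 1 − exp(−r(21 + dM)), with M the weeks of maintenance and d the fraction of events captured there.

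The documents give neither r nor d; both are assumptions. Setting d = 0 is the case most favourable to EZN-2279.

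| r per week | Adagen, L = 3 | Adagen, L = 12 | EZN-2279, d = 0 |
|---|---|---|---|
| 0.02 | 5.8% | 21.3% | 34.3% |
| 0.05 | 13.9% | 45.1% | 65.0% |
| 0.20 | 45.1% | 90.9% | 98.5% |

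At r = 0.05 and d = 0.5, EZN-2279 reaches 81.7% at week 47. For any equal rate and any lead-in shorter than 21 weeks, the planned percentage is higher on EZN-2279, even if maintenance captures nothing.

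**4. Where the EZN-2279 time lies.** The T-11 visit is 10 weeks after the first dose (Day 71) and the T-21 visit is 20 weeks after it (Day 141).

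| Total weeks T | Weekly, 10/T | Two-weekly or closer, 20/T | 13-weekly, remainder |
|---|---|---|---|
| 47 | 21.3% | 42.6% | 57.4% |
| 104 | 9.6% | 19.2% | 80.8% |
| 156 | 6.4% | 12.8% | 87.2% |

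**5. If a reader computes a rate.** Let f be the fraction of minor events captured in maintenance, relative to closer visits. The pooled rate as a share of its true value is (20 + f(T − 20))/T.

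| T | f = 0.3 | f = 0.5 | f = 0.8 |
|---|---|---|---|
| 47 | 28.1/47 = 60% | 33.5/47 = 71% | 41.6/47 = 89% |
| 104 | 45.2/104 = 43% | 62/104 = 60% | 87.2/104 = 84% |
| 156 | 60.8/156 = 39% | 88/156 = 56% | 128.8/156 = 83% |

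At f = 1 there is no distortion. Counting 21 weeks instead of 20 as closely visited changes the middle column only to 72%, 60% and 57%.

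**The case against.** A reader might infer that EZN-2279 is bound to look better tolerated per unit time. The documents do not support that. No per-time AE measure is planned, and step 3 shows that the planned count leans the other way. The deflation in step 5 arises only if someone builds a rate that the SAP does not describe and if capture in maintenance is in fact lower. Nor would the planned pooled table show events falling off over time, because a pooled table shows no trend.

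Several provisions limit the loss. Patients are told to report any AE during the study (Protocol 10.4.4). Serious events have 24-hour reporting (Protocol 12.4). Allergic signs, including injection-site reactions, go to the sponsor within 48 hours whether serious or not (Protocol 12.4.1). Sites need not dispense a full 13-week supply, so extra contacts are possible. All of this stands, although for non-serious events the site must first hear of them. The capture fraction has no basis in the documents and could be close to 1.

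The lead-in is not perfectly weekly either. The procedures listed for Adagen PK Day 1 include no AE assessment, which leaves two weeks between listed assessments in a minimum lead-in.

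Finally, the analysis is descriptive in about six evaluable patients, all AEs are listed with onset dates, and the table shells are in a companion document not available here. A careful reader could split the events by hand, and the shells might already do so. That lowers the stakes, but the SAP text should still specify the split.

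**Conclusion.** The two summaries, as SAP 7.3 describes them, are not comparable. This rests on the documents alone: summaries by drug only, through maintenance, with exposure at least 7 times the minimum lead-in and assessment intervals that go from one week to 13 ± 3 weeks.

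The direction of distortion depends on the reading. As planned percentages, EZN-2279 is inflated relative to Adagen; the figures in step 3 assume equal constant rates. As an exposure-adjusted rate, EZN-2279 would be deflated by any loss of capture in maintenance: to about 71% of its true value at week 47 and 56-60% at 2-3 years if capture is 50%, or to 60-89% and 39-84% if it is 30-80%. Those capture values are assumptions.

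This is a low-cost improvement to how safety is presented. It does not show that a planned statistic favours EZN-2279.

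**What to change.** In SAP 7.3, tabulate EZN-2279 AEs separately for the treatment period (T-1 to T-21) and the maintenance period, with an overall column, matching the exposure split in SAP 7.2. Add events per patient-week for each period and for the Adagen lead-in.

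Base any comparison with Adagen on treatment-period rates, with T-1 to T-11 shown as the closest match in visit frequency. Rates are needed because that window is about 10 weeks against a lead-in of at least 3, so a patient count would still be unequal.

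Add a footnote that one-hour post-dose observation is stated for EZN-2279 site doses through T-9, while for Adagen post-dose monitoring is stated only for the initial dose. Acute reactions may therefore be detected more readily on EZN-2279 in those weeks, and the split does not remove that difference.

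The cost is a little more programming from onset dates already collected, and smaller counts per column. No new visits or data are needed.
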